Appendix 1: Symptoms and Pain Questionnaire

1. Have you experienced foreign body sensation?

Yes No If yes, OD OS OU

If yes, did it start immediately after drop instillation?

OD: Yes No Don't remember

OS: Yes No Don't remember

How long did it last?

OD: 1 min or less 2 to 5 min 6-10 min > 10 min

OS: 1 min or less 2 to 5 min 6-10 min > 10 min

How severe was it?

OD: Mild Moderate Severe

OS: Mild Moderate Severe

Place a vertical mark on the line below to indicate the severity.

OD

No pain | _____ | Very Severe Pain

OS

No pain | _____ | Very Severe Pain

2. Have you experienced stinging/burning?

Yes No If yes, OD OS OU

If yes, did it start immediately after drop instillation?

OD: Yes No Don't remember

OS: Yes No Don't remember

How long did it last?

- OD: 1 min or less 2 to 5 min 6-10 min > 10 min
- OS: 1 min or less 2 to 5 min 6-10 min > 10 min

How severe was it?

- OD: Mild Moderate Severe
- OS: Mild Moderate Severe

Place a vertical mark on the line below to indicate the severity.

OD

No pain | _____ | Very Severe Pain

OS

No pain | _____ | Very Severe Pain

3. Have you experienced any pain/discomfort?

- Yes No If yes, OD OS OU

If yes, did it start immediately after drop instillation?

- OD: Yes No Don't remember
- OS: Yes No Don't remember

How long did it last?

- OD: 1 min or less 2 to 5 min 6-10 min > 10 min
- OS: 1 min or less 2 to 5 min 6-10 min > 10 min

How severe was it?

- OD: Mild Moderate Severe
- OS: Mild Moderate Severe

Place a vertical mark on the line below to indicate the severity.

OD

No pain | _____ | Very Severe Pain

OS

No pain | _____ | Very Severe Pain

4. Overall, how satisfied have you been with the results of your cataract surgery in your ...?

OD

OS

Very dissatisfied

Very dissatisfied

Dissatisfied

Dissatisfied

Neither satisfied nor dissatisfied

Neither satisfied nor dissatisfied

Satisfied

Satisfied

Very satisfied

Very satisfied

5. Given your postoperative vision/outcome, if you had to do it all over again, would you select:

LessDrops

3-Drops

6. Given your postoperative experience, if you had to do it all over again, would you select:

LessDrops

3-Drops

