3.3.2. Measurements and evaluations

1. Visit 1: Informed consent process will be conducted at this visit. Assessments include uncorrected and best-corrected ETDRS visual acuity at 4 m (UCVA / BCVA), manifest refraction, intraocular pressure (IOP) using Goldman tonometer, and slit lamp examination including dilated fundus exam, cataract density and type, ultrasonic central corneal pachymetry (UCCP), and optical coherence tomography (OCT). Symptoms (foreign body sensation (FBS) and burning/stinging) and pain in each eye will be assessed and compared with that of the fellow eye. Any testing that is part of the site's standard of care preoperative cataract surgery evaluation may be performed prior to the informed consent being signed provided these tests are conducted within 90 days of the surgery and notation of the date performed is entered onto the source document.

The first eye undergoing surgery will be randomized to either Group A (test) or Group B (control). Randomization will ensure that an equal number of first eyes are test and control.

2. Visit 2: The surgeon may use his preferred cataract extraction technique (manual or laser). The lens will be implanted in the bag. The following information will be captured the day of surgery: phaco technique (manual or laser), phacoemulsification time, cumulative dissipated energy (CDE), estimated fluid used, and duration of surgery (from opening/creating the incision to hydration of the wound).
3. Visit 3: Slit lamp examination, UCVA, IOP, UCCP, patient satisfaction, symptoms and pain will be assessed.
4. Visit 4 and 5: Slit lamp examination, UCVA, BCVA, IOP, UCCP, OCT, patient satisfaction, symptoms and pain will be assessed as well as presence of rebound inflammation. Rebound inflammation will be diagnosed based on the following symptoms: ocular pain, blurry vision, light sensitivity and redness; and slit lamp examination showing anterior chamber cells and/or flare. Rebound inflammation will be treated with Prednisolone acetate 1% to QID for 2 days, continued BID for a week and QD for one additional week then discontinued.

All adverse events and complaints will be monitored and recorded at all study visits.

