Appendix 1 summarizes the standard evaluation procedures.

Table 1. Visits and Study Assessments

Study Assessments	Visit 1 Preoperative	Visit 2 Operative	Visit 3 Day 1	Visit 4 Day 15 ±2	Visit 5 Day 30 ±5
Inclusion/Exclusion Criteria	x				
Consent Subject	x				
Patient demographics (age, gender, race, ethnicity)	x				
Manifest Refraction	x		x	x	x
UCDVA	x		x	x	x
BCDVA	x			x	x
Goldman Tonometry (IOP)	x		x	x	x
Complete slit lamp exam	x		x	x	x
Dilated fundus exam	x				†
Cataract density	x				
Ultrasonic central corneal pachymetry	x		x	x	x
Central macular thickness (OCT)	x			x	x
Use of femtosecond laser		x			
Phacoemulsification time		x			
CDE		x			
Estimated fluid used		x			
Duration of surgery		x			
Record Lens Model Implanted		x			
Patient satisfaction					x
Symptoms (FBS & burning/stinging)	x		x	x	x

Pain	x		x	x	x
Adverse events / device deficiency		x	x	x	x

x To be performed as scheduled

† To be performed as deemed necessary by the investigator.

4. Study Completion Criteria

- 4.1. Patient Completion of Study: If a study patient has completed the final visit (Visit 5) of the study, he/she is considered to have completed the study.
- 4.2. Patient Discontinuation/Withdrawal: Each study patient may voluntarily discontinue the study at any time they choose. Study patients who cannot complete the study for administrative reasons (e.g., non-compliance, failure to meet visit schedule, etc.) will be discontinued from the study. Study patients discontinued during the enrollment phase (prior to surgery) of the study will be replaced.
- 4.3. Patient Termination: A study patient will be terminated if the study patient develops any severe adverse event that may be related to the study. A study patient will receive appropriate treatment at the discretion of the investigator. Notification of termination will be clearly documented. These study patients are considered to have completed the study and will not be replaced.
- 4.4. Study Termination: The investigator with appropriate notification may terminate the study. If, after clinical observations, the investigator feels that it may be unwise to continue the study, he may stop the study.
- 4.5. Study Completion: The study will be complete when all enrolled patients have completed Visit 5 or have been terminated from the study.

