4. **Anterior Chamber Cells and Flare:** Postoperatively at day 1, 15 and 30, anterior chamber cells and flare will be evaluated before tonometry or any other test that would affect examination. Both will be graded by the examiner using the following scale:

Number of Cells	Flare
0- none	0- none
1 - 1-5 cells	1 - Tyndall effect barely discernible
2 - 6-15	2 - mild Tyndall effect
3 - 16-30	3 - strong Tyndall effect
4- > 30	4 - intense Tyndall effect - aqueous has milky white appearance

5. **Macular thickness** (preop, days 15 and 30): It will be measured before tonometry or any other test that would affect OCT measurements. Macular thickness will be performed using SD-OCT (Cirrus [Zeiss]) following the manufacturer's recommendations. One 512 x 128 Macular Cube scan will be acquired per eye.
6. **Central corneal ultrasound pachymetry:** To be measured preop, and at day 1, 15 and 30. Three measurements will be taken and recorded as well as the average of the 3 measurements taken.

- 7. Intraocular pressure measurements:** IOP measurements will be measured at the Screening visit and at day 1, 15 and 30 postoperatively using Goldmann tonometry.
- 8. Questionnaires:** Examiner will read aloud the questions to the subject and will record the response given by the subject in the source document. For the Visual Analog Scale (VAS), the examiner will ask the patient to place a vertical mark on the line for each question then use ruler (cm) to calculate the score with 1 mm equal to 0.1 cm. A decimal value should be recorded (i.e., 2.1, 4.0). Questions 4 to 6 will be asked only at the Day 30 visit.
- 9. Dilated fundus examination:** To be performed preoperatively and at Day 30 (if deemed necessary by the investigator) using the investigator's preferred technique.

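### The VAS lines for foreign body sensation and stinging/burning carry pain end labels, and 5.3.2 does not say which item is analysed; zero to four of 11 secondary endpoints are exposed (minor)

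*Combined protocol and SAP*

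**What the plan says.** The questionnaire in Appendix 1 asks three symptom questions: "Have you experienced foreign body sensation" (question 1), "Have you experienced stinging/burning" (question 2) and "Have you experienced any pain/discomfort" (question 3). Each runs through Yes/No with the eye concerned, onset, duration and a Mild/Moderate/Severe grade. Each then instructs the patient: "Place a vertical mark on the line below to indicate the severity". The line that follows, for each eye and under all three questions, reads "No pain | _____ | Very Severe Pain".

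Appendix 1, item 8, has the patient "place a vertical mark on the line for each question then use ruler (cm) to calculate the score", recorded as a decimal with 1 mm equal to 0.1 cm.

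Elsewhere the protocol keeps the symptoms apart from pain. Section 3.3.2 (Visit 1) says: "Symptoms (foreign body sensation (FBS) and burning/stinging) and pain in each eye will be assessed and compared with that of the fellow eye". Table 1 has one row for "Symptoms (FBS & burning/stinging") and another for pain.

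Section 5.3.2 lists 11 secondary endpoints. Four concern FBS or burning/stinging: for each symptom, a proportion of subjects marked with a '0', and a change from baseline. None says which questionnaire item supplies the value.

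**The concern.** The printed labels suit question 3 but not questions 1 and 2. A gritty eye that does not hurt belongs at the 'No pain' end if the labels are taken at face value, and the ruler then gives a score at or near 0 for a symptom that is present.

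The background section names patient comfort as a possible advantage of a single combined drop, and these endpoints are among those that could show it. If real symptoms are pulled toward 0 in both eyes, a true difference between regimens becomes harder to see, whichever way it runs. Section 5 states no equivalence margin, so a diluted null result could be misread as similar tolerability.

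The unnamed source item is a second gap, and it does not depend on how patients mark the line. The two proportion bullets for FBS and burning/stinging also speak of subjects reporting the symptom, with '0' in brackets, whereas the parallel pain bullet speaks of reporting none.

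**Working it through.** The plan gives no figure for these endpoints that could be reproduced. The calculation in 5.1 (30 subjects, 35 enrolled) is for macular thickness and uses nothing from the questionnaire. The check is a comparison of texts, a count, and some algebra.

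**1. Label against construct.**
- Question 1: FBS, on a line running from no pain to very severe pain. Mismatch.
- Question 2: stinging/burning, on the same line. Mismatch, arguably smaller than for FBS.
- Question 3: pain/discomfort, on the same line. It fits pain; discomfort without pain is a milder mismatch.

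**2. Route from label to score.** Item 8 measures the position of the mark. A mark at the left end is 0; a mark 1 mm away is 0.1. A change score is therefore affected by marks at or near the end. A VAS '0' proportion is affected only by marks exactly at it.

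**3. Candidate source items.**
- VAS: has a numeric scoring rule (item 8).
- Mild/Moderate/Severe: no numeric codes and no 'none' option on the form.
- Yes/No with eye: no numeric code, but it can identify absence.

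A change from baseline needs a graded score, so the VAS is the most likely source for the two change endpoints. For the '0' proportions, the pain bullet in 5.3.2 ties its '0' to the eye pain/discomfort measure, and the next bullet calls that measure a score. This suggests a VAS value for the parallel symptom bullets too, but does not settle it.

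**4. Count of exposed endpoints.** Table 1 schedules the symptoms at Visits 1, 3, 4 and 5: one baseline and three postoperative visits (Days 1, 15 and 30).
- Change from the Mild/Moderate/Severe item, '0' from Yes/No: 0 of 11 endpoints.
- Change from the VAS, '0' from Yes/No: 2 of 11 (2/11 = 18%), or 2 × 3 = 6 postoperative comparisons.
- All four from the VAS: 4 of 11 (4/11 = 36%), or 4 × 3 = 12 postoperative comparisons.

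**5. Direction of the effect.** Suppose a share m of symptomatic eyes is marked 0, unrelated to severity, visit or regimen. The observed mean VAS is then the true mean × (1 − m), and the observed share above 0 is the true share × (1 − m). Both eyes scale alike, so the between-eye difference also shrinks by (1 − m). If mainly the milder symptoms are marked 0, the mean shrinks by less than that. If m differed between regimens, the two eyes would scale differently and the comparison could be biased. The documents give no value for m, so this shows direction only.

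**The case against.** The strongest reply is that the form guards against the error. The examiner reads each question aloud; the patient has just answered about that symptom, its duration and its grade, and is then told to mark severity. Someone who has just ticked Moderate for FBS is unlikely to mark 0. For stinging and burning, the distance from pain is small in any case. This stands as a limit on the size of the effect. It does not make the labels right: the instruction does not name the symptom again, and the last words the patient sees before marking are about pain.

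It is also fair to say that, with no source item named, one cannot assert that any endpoint uses these lines. That stands in full, which is why the range starts at zero.

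A reader might infer three stronger things, none of which the documents support:
- **That the labels favour one regimen.** Both eyes are marked on the same labels, so bias needs the share of painless symptoms to differ between regimens. Nothing in the documents shows that it does.
- **That the loss of sensitivity can be quantified.** Any factor would rest on an assumed m and on marking at 0 being unrelated to severity.
- **That the item will be chosen after the data are seen.** The plan leaves this possible; it does not say that it will happen.

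**Conclusion.** The concern holds as a minor fault in the instrument as written. The end labels under questions 1 and 2 do not match what is being rated, and a patient who follows them can be scored at or near 0 while having the symptom. The plausible consequence is some dilution of a between-eye tolerability difference, of a size the documents do not allow one to estimate.

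Zero to four of the 11 secondary endpoints are exposed. Two is the most likely minimum, on the assumption that the change scores come from the VAS. Four applies if '0' is also a VAS value. The milder mismatch in question 3 is not in that count. The primary endpoint, macular thickness on OCT, and the sample size are untouched.

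**What to change.** **Form.** Print symptom-specific end labels:
- question 1: 'No foreign body sensation' to 'Very severe foreign body sensation';
- question 2: 'No burning/stinging' to 'Very severe burning/stinging';
- question 3: 'No pain/discomfort' to 'Very severe pain/discomfort'.

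**Section 5.3.2.** Reword the two proportion bullets as 'reporting no FBS' and 'reporting no burning/stinging'. State that '0' and the change score both come from the relabelled VAS in cm, for FBS, burning/stinging and pain/discomfort alike. Moving only FBS and burning/stinging to the Yes/No item would break the parallel with the pain bullet and is not needed once the labels are right.

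**Cost.** Six relabelled lines (three questions × two eyes) and a short edit to the six symptom and pain bullets. The real downside arises if forms are already in use: marks on the old labels are not comparable with marks on the new ones, and a patient whose baseline was taken on the old form has no clean change score on the new one. For patients with such marks, report the Yes/No item as a supporting analysis. Naming the source item and clarifying '0' loses no data and can be done at any time before analysis.
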